#### **4.5 Data Monitoring Committee (DMC) Activities**

An independent external Data Monitoring Committee (DMC) is used to review unblinded safety data at regular intervals during the conduct of the study. The DMC will provide recommendation to an AbbVie Point of Contact on whether to continue, modify, or terminate studies after each review. When needed, high level unblinded efficacy data may also be requested by the DMC and be reviewed so that the DMC can assess benefit:risk of any emerging safety differences.

### **5.0 Analysis Populations and Analysis Windows**

#### **5.1 Analysis Populations**

##### **Full Analysis Set (FAS)**

The Full Analysis Set (FAS) includes all randomized subjects who received at least one dose of study drug. The FAS will be used for all efficacy and baseline analyses.

### **Per Protocol Analysis Set**

The Per Protocol Analysis Set represents a subset of the FAS and consists of all FAS subjects who did not meet any major protocol deviations during Period 1 of the study. Additional analysis of the primary efficacy endpoint will be conducted on the Per Protocol analysis set, in order to evaluate the impact of major protocol deviations.

Major protocol deviations will be identified prior to database lock.

### **Safety Analysis Set**

The Safety Analysis Set consists of all subjects who received at least one dose of study drug. For the Safety Analysis Set, subjects are assigned to a treatment group based on the "as treated" treatment group, regardless of the treatment randomized. The "as treated" is determined by the treatment the subject received during the majority of the subject's drug exposure time in the analysis period.

## **5.2 Analysis Windows**

### **Definition of Study Days (Days Relative to the First Dose of Study Drug)**

Study Days are calculated for each collection date relative to the date of the first dose of study drug. It is defined as the number of days between the date of the first dose of study drug and the collection date. Study days are negative values when the collection date of interest is prior to the first study drug dose date. Study days are positive values when the collection date of interest is on or after the first study drug dose date. The day of the first dose of study drug is defined as Study Day 1, while the day prior to the first study drug dose is defined as Study Day -1 (there is no Study Day 0). Study days are used to map actual study visits to the protocol-specified study visits.

### **Definition of Analysis Windows**

The following rules will be applied to assign actual subject visits to protocol-specified visits. For each protocol-specified study visit, a target study day will be identified to

represent the corresponding visit along with a window around the target day. Windows will be selected in a non-overlapping fashion so that a collection date does not fall into multiple visit windows. If a subject has two or more actual visits in one visit window, the visit closest to the target day will be used for analysis. If two visits are equidistant from the target day, then the later visit will be used for analysis.

The visit window and the target study day for each protocol-specified visit in Period 1 are displayed in [Table 1](#) and [Table 2](#) (depending on the different visit schedules of different endpoints). Visit windows for protocol-specified visits in Period 2 are defined similarly.

**Table 1. Analysis Windows for Efficacy Analysis for Period 1 (for ACR Components and Morning Stiffness) and Safety Analysis for Period 1 (for Labs and Vital Signs)**

Protocol Specified Visit Week	Lower Bound	Target Day	Upper Bound
Baseline	-99	1 a	1
1	2	8	11
2	12	15	22
4	23	29	43
8	44	57	71
12	72	85	min (99, first dose date of Period 2)

a. Day of first dose of study drug.

**Table 2. Analysis Windows for Efficacy Analysis for Period 1 (for EQ-5D-5L, SF-36, FACIT-F and RA-WIS)**

Protocol Specified Visit Week	Lower Bound	Target Day	Upper Bound
Baseline	-99	1 a	1
4	2	29	57
12	58	85	min (127, first dose date of Period 2)

a. Day of first dose of study drug.

## **6.0 Demographics, Baseline Characteristics, Medical History, and Previous/Concomitant Medications**

### **6.1 Demographics and Baseline Characteristics**

Demographic and baseline characteristics information will be collected at the Baseline visit of the study and will be summarized for the FAS. The number of observations, mean, standard deviation, median, minimum and maximum will be summarized for continuous variables. Categorical or discrete variables will be summarized via frequencies and percentages. Summary statistics will be computed for each treatment group and overall.

#### **Main Demographic and Baseline Characteristics**

- Sex (male/female)
- Age (years)
- Age Categories (< 40, [40, 65], ≥ 65 years)
- Race (White, Black or African American, American Indian or Alaska Native, Native Hawaiian or Other Pacific Islander, Asian, Other)
- Geographic Region (North America, South/Central America, Western Europe, Eastern Europe, Asia, Other)
- Ethnicity (Hispanic or Latino, Not Hispanic or Latino)
- Weight (kg)
- Weight Categories (< 60 kg, ≥ 60 kg)
- Height (cm)
- Body Mass Index (BMI) (kg/m^2)
- Body Mass Index (BMI) Category (kg/m^2) (BMI < 25 vs BMI ≥ 25)

#### **RA Medical History and Characteristics**

- Duration of RA Symptoms in years
- Duration of RA Diagnosis in years

- Duration of RA Diagnosis Categories (< 5 year or ≥ 5 year)
- Prior exposure to bDMARDs (Yes or No)

### **ACR and/or DAS Components at Baseline**

- Tender joint count (TJC68) defined as the number of tender joints out of 68 assessed joints
- Swollen joint count (SJC66) defined as the number of swollen joints out of 66 assessed joints
- Tender joint count (TJC28) defined as the number of tender joints out of 28 assessed joints used for DAS28 calculation
- Swollen joint count (SJC28) defined as the number of swollen joints out of 28 assessed joints used for DAS28 calculation
- Physician's global assessment of disease activity (mm on a 100-mm horizontal visual analogue scale [VAS])
- Patient's assessment of pain within last week (mm on a 100-mm horizontal (VAS)
- Patient's global assessment of disease activity within last 24 hours (mm on a 100-mm horizontal VAS)
- Health Assessment Questionnaire Disability Index of the (HAQ – DI) (range: 0 to 3)
- High sensitivity C-reactive protein (hsCRP) (mg/L)
- Erythrocyte sedimentation rate (ESR) (mm/hr)

### **Other Baseline RA Disease Characteristics**

- Anti-cyclic citrullinated peptide (Anti-CCP) (units)
- Anti-CCP status: Positive or Negative
- Rheumatoid Factor (RF) (units)
- Rheumatoid Factor (RF) status: Positive or Negative
- Percentage of subjects on oral steroid at baseline
- Oral steroid dose (prednisone equivalent) at baseline

- DAS28 [hsCRP]
- DAS28 [ESR]
- DAS28 Categories:
  - DAS28 > 5.1 (High Disease Activity)
  - DAS28 ≤ 5.1
- Clinical Disease Activity Index (CDAI)
- CDAI categories:
  - CDAI > 22 (High Disease Activity)
  - CDAI ≤ 22
- Simplified Disease Activity Index (SDAI)
- SDAI categories:
  - SDAI > 26 (High Disease Activity)
  - SDAI ≤ 26

### **Patient Report Outcomes at Baseline**

- Morning stiffness (severity and duration)
- Functional Assessment of Chronic Illness Therapy-Fatigue (FACIT-F)
- Work Instability Scale for Rheumatoid Arthritis (RA-WIS)
- 36-Item Short Form Health Survey (SF-36) Version 2: physical component summary, mental component summary and the 8 sub-domain scores
- EQ-5D-5L

### **Clinical Tests at Screening**

- Chest x-ray
- ECG
- Tuberculin PPD skin test, QuantiFERON TB Gold test
- Hepatitis Testing
- Serum pregnancy test

### **Immunization History**

- BCG immunization
- Herpes Zoster immunization
- Hepatitis B immunization

### **Tobacco/Nicotine and Alcohol Use**

- Tobacco/Nicotine Use [user, ex-user, non-user, unknown]
- Alcohol Use [drinker, ex-drinker, non-drinker, unknown]

## **6.2 Medical History**

Medical history data will be summarized and presented for FAS population using body systems and conditions/diagnoses as captured on the CRF. The body systems will be presented in alphabetical order and the conditions/diagnoses will be presented in alphabetical order within each body system. The number and percentage of subjects with a particular condition/diagnosis will be summarized for each randomized treatment group as well as overall. Subjects reporting more than one condition/diagnosis within a body system will be counted only once for that body system. No statistical comparison will be performed for medical history reporting.

## **6.3 Prior Treatment and Concomitant Medications**

Prior and concomitant medications will be summarized by each randomized treatment group as well as overall for FAS. Prior medications are those medications taken prior to the first dose of study drug. This includes medications with a start date before the first study drug administration date, regardless of the end date of these medications.

Medications taken on the day of the first dose of study drug are not counted as prior medications. Concomitant medications are those medications, other than study drug, taken after the first dose of study drug and within 1 day of the last dose of study drug. This includes medications with a start date between first study drug administration and last study drug administration + 1 day, as well as, medications with a start date prior to

first dose of study drug and which are ongoing after first dose of study drug. Medications taken on the day of the first dose of study drug are counted as concomitant medications.

The number and percentage of subjects who received a prior medication and the number and percentage of subjects who received a concomitant medication will be tabulated separately by the generic name assigned by the most current version of the World Health Organization (WHO) Drug Dictionary.

#### **6.4 Protocol Deviations**

Protocol deviations are categorized as follows based on ICH deviation criteria:

- Those who entered the study even though they did not satisfy the entry criteria
- Those who developed withdrawal criteria during the study and were not withdrawn
- Those who received the wrong treatment or incorrect dose, and
- Those who received an excluded or prohibited concomitant medication.

The protocol deviations listed above will be summarized and listed by treatment group.

#### **7.0 Patient Disposition**

The following will be summarized by randomized treatment group as well as overall:

- number of subjects randomized,
- number of subjects included in key analysis populations (Full Analysis Set and Per Protocol Analysis Set for primary efficacy analysis, Safety Analysis Set for Period 1),
- number of subjects who completed Period 1 study participation,
- number of subjects who entered Period 2,
- number of subjects on-going in Period 2 (if applicable),
- number of subjects who completed overall study (Period 1 and Period 2) participation.

This summary will be repeated by site.

Premature discontinuation details will be further summarized separately for Period 1 and Period 2 as follows.

### **Period 1**

The number and percentage of subjects completed Period 1 and prematurely discontinued in Period 1 will be summarized by randomized treatment group, separately by study drug and study participation completion/discontinuation, with the primary reason for discontinuation collected from CRF by the following categories:

- Adverse event (AE)
- Withdrew consent
- Lost to follow-up
- Lack of efficacy
- Other.

Subjects may have more than one reason for discontinuing, but only the primary reason will be summarized.

In addition, the number and percentage of subjects enrolled in Period 2 will also be summarized by randomized treatment group.

### **Period 2**

Period 2 patient dispositions and reason for discontinuation will be summarized for overall and by treatment regimen when entering Period 2 defined as follows:

1. Upadacitinib 15 mg QD
2. Upadacitinib 30 mg QD

Among the subjects who entered Period 2 participation (regardless of whether subject prematurely discontinued study drug in Period 1), the number and percentage of subjects completed, on-going (if applicable), and prematurely discontinued study participation in Period 2 will be summarized. Among the subjects who entered Period 2 upon completion of study drug in Period 1, the number and percentage of subjects completed, on-going (if applicable), and prematurely discontinued study drug in Period 2 will be summarized.

For subjects who prematurely discontinued study drug or study participation, the primary reason as well as all reasons for discontinuation will be summarized by the following categories (as collected in CRF):

- Adverse event (AE)
- Withdrew consent
- Lost to follow-up
- Lack of efficacy
- Other.

### **Summary of Dose Switch from Upadacitinib 30 mg QD to 15 mg QD**

Starting with Amendment 6, all subjects will receive open-label upadacitinib 15 mg QD, including those currently on upadacitinib 30 mg QD. The visit at which dose switch occurs could be different for each subject. For subjects on upadacitinib 30 mg QD in Period 2, the number and percentage of subjects switching to upadacitinib 15 mg QD at each visit will be summarized.

## **8.0 Study Drug Exposure and Compliance**

### **8.1 Study Drug Exposure**

The duration of exposure to study drug will be summarized for the safety analysis set by the following groups.

1. Placebo

2. Upadacitinib 15 mg QD

This includes upadacitinib 15 mg QD exposure from subjects starting on upadacitinib 15 mg QD and subjects switching from placebo to upadacitinib 15 mg QD.

3. Upadacitinib 30 mg QD

This includes upadacitinib 30 mg QD exposure from subjects starting on upadacitinib 30 mg QD and subjects switching from placebo to upadacitinib 30 mg QD. Exposure is censored at time of dose switch from upadacitinib 30 mg QD to upadacitinib 15 mg QD.

4. upadacitinib 15 mg QD switched from upadacitinib 30 mg QD

This includes upadacitinib 15 mg QD exposure from subjects who switched dose from upadacitinib 30 mg QD to upadacitinib 15 mg QD.

Starting with Amendment 6, all subjects will receive open-label upadacitinib 15 mg QD, including those currently on upadacitinib 30 mg QD. Exposure to upadacitinib 30 mg QD (Group 3) will be censored prior to the day subject received the first dose of upadacitinib 15 mg QD, and subsequent exposure to upadacitinib 15 mg QD will be summarized under a separate group (Group 4).

The duration of exposure to study drug will be summarized for each group as specified above, with the number of subjects, mean, standard deviation, median, minimum and maximum values. In addition, the number and percentage of subjects exposed to study drug will be summarized for the following cumulative duration intervals.

- $\geq 2$  weeks
- $\geq 1$  month
- $\geq 3$  months
- $\geq 6$  months

- $\geq 9$  months
- $\geq 12$  months
- $\geq 18$  months
- $\geq 2$  years
- $\geq 2.5$  years
- $\geq 3$  years
- $\geq 4$  years

## **8.2 Compliance**

Study drug compliance will be summarized for each treatment group for Period 1. The compliance is defined as the number of tablets taken (i.e., the difference between the number of tablets dispensed and the number of tablets returned) during the subject's participation in Period 1 divided by the number of days that the subject was in the Treatment Phase of Period 1.

## **9.0 Efficacy Analysis**

### **9.1 General Considerations**

There are two sets of planned efficacy analysis: efficacy analysis for Period 1 and long-term efficacy analysis. All efficacy analyses will be carried out using the FAS population.

#### **9.1.1 Efficacy Analysis at Different Phases of the Study**

##### **Efficacy Analysis for Period 1**

Standard efficacy analysis by randomized treatment groups (upadacitinib 15 mg QD, upadacitinib 30 mg QD and the combined placebo groups) will be performed on efficacy data for Period 1 (up to Week 12). No protocol-defined treatment switching will occur prior to the time point. Formal statistical inference will be generated, and results from this set of analysis will be used as the key efficacy findings of this study.

### **Long-Term Efficacy Analysis**

Long-term efficacy analysis will be performed on As Observed data (defined in Section 9.1.2) by randomized treatment group sequence as described below:

1. Upadacitinib 15 mg QD
2. Upadacitinib 30 mg QD
3. Placebo → Upadacitinib 15 mg QD
4. Placebo → Upadacitinib 30 mg QD.

There will be no statistical testing; only descriptive statistics and confidence intervals will be provided.

Starting with Amendment 6, all subjects will receive open-label upadacitinib 15 mg QD, including those currently on upadacitinib 30 mg QD. For long-term efficacy analysis, subjects will continue to be summarized under the treatment sequences as described above, regardless of dose switch – i.e., for treatment sequences 2 and 4, data collected after dose switch will continue to be summarized under the same treatment sequences. The visit at which dose switch occurs could be different for each subject. The first and last visits at which dose switch occurs will be noted in the summary.

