5.5.5 Blinding

5.5.5.1 Blinding of Investigational Product

All AbbVie personnel with direct oversight of the conduct and management of the trial (with the exception of AbbVie Drug Supply Management Team), the Investigator, study site personnel, and the subject will remain blinded to each subject's treatment throughout the study. Starting with Amendment 6, all subjects will receive open-label upadacitinib 15 mg QD, including those currently on upadacitinib 30 mg QD.

In order to maintain the blind, the upadacitinib (ABT-494) tablets and placebo tablets provided for the study will be identical in appearance. The IRT will provide access to unblinded subject treatment information in the case of medical emergency.

In the event of a medical situation that requires unblinding of the study drug assignment, the Investigator is requested to contact the AbbVie Therapeutic Area Medical Director prior to breaking the blind. However, if an urgent therapeutic intervention is necessary which warrants breaking the blind prior to contacting the AbbVie Therapeutic Area Medical Director, the Investigator can directly access the IRT system to break the blind without AbbVie notification or agreement. Unblinding is available in the IRT system via the Unblind Subject transaction, which is available only to the Investigator. If the IRT system is unavailable, unblinding may occur by contacting EndPoint technical support via either phone (preferred) or email ([contact]). For country-specific phone numbers, please see the following website: <http://www.endpointclinical.com/help-desk/>. In the event that the blind is broken before notification to the AbbVie Therapeutic Area Medical Director, AbbVie requests that the AbbVie Therapeutic Area Medical Director be notified within 24 hours of the blind being broken. The date and reason that the blind was broken must be conveyed to AbbVie and recorded on the appropriate eCRF.

An unblinded analysis will be conducted after all subjects have completed Period 1 (Week 12) for the purpose of regulatory submission. Study sites and subjects will remain blinded for the duration of the study.

Starting with Amendment 6, all subjects will receive open-label upadacitinib 15 mg QD, including those currently on upadacitinib 30 mg QD. Study sites and subjects will no longer be blinded after this point.

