8.0 Statistical Methods and Determination of Sample Size

8.1 Statistical and Analytical Plans

An unblinded analysis will be conducted after all subjects have completed Period 1 (Week 12) for the purpose of regulatory submission. Study sites and subjects will remain blinded for the duration of the study.

Completed and specific details of the statistical analysis will be described and fully documented in the Statistical Analysis Plan (SAP). The SAP will be finalized prior to the database lock for the analysis at the end of Period 1. The statistical analyses will be performed using SAS (SAS Institute Inc., Cary, NC, USA).

Starting with Amendment 6, all subjects will receive open-label upadacitinib 15 mg QD, including those currently on upadacitinib 30 mg QD. The details for handling the change in dose in analysis will be described in the Statistical Analysis Plan (SAP) for final reporting.

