### **Discontinuation of Study Drug and Continuation of Study Participation (Period 1 and Period 2)**

Subjects may discontinue study drug treatment, but may choose to continue to participate in the study (refer to protocol for additional details). Subjects who prematurely discontinue study drug should complete a Premature Discontinuation (PD) visit as soon as possible, preferably within 2 weeks. To minimize missing data for efficacy and safety assessments, subjects who prematurely discontinue study drug treatment should continue to be followed for all regularly scheduled visits as outlined in the protocol, unless subjects have decided to discontinue study participation entirely (withdrawal of informed consent). Subjects should be advised on the continued scientific importance of their data even if they discontinue treatment with study drug early. Following discontinuation of study drug, the subject should be treated in accordance with the investigator's best clinical judgment irrespective of whether the subject decides to continue participation in the study. As the subject has discontinued study drug, all rescue and efficacy driven discontinuation criteria no longer apply. This includes the 20% TJC/SJC calculations at Week 24 and visits thereafter, as well as the CDAI calculation at Week 24, if applicable. If at any point a subject no longer wants to provide assessments (withdrawal of informed consent) following discontinuation of study drug, a second PD visit is not required.

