**As Observed (AO)**

The AO analysis will not impute values for missing evaluations. Regardless of treatment switching or premature discontinuation of study drug, all observed data will be used in the analysis. The AO analysis will be applied to long-term efficacy analysis.

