### **10.3.3 Analysis of Long-Term Laboratory Data**

#### **10.3.3.1 Assessment of Mean Change from Baseline in Clinical Laboratory Variables**

Analyses of mean change from baseline in continuous hematology, chemistry, and urinalysis variables which are measured longitudinally will be performed by visits and by "as treated" treatment group sequences as described in Section 10.1. For each change from baseline analysis, the following summary statistics will be presented for each treatment group: sample size, baseline mean, visit mean, and the mean, standard deviation, and median of the changes from baseline.

Starting with Amendment 6, all subjects will receive open-label upadacitinib 15 mg QD, including those currently on upadacitinib 30 QD. Mean change from baseline in laboratory values for subjects who switched from upadacitinib 30 mg QD to 15 mg QD will be censored at the time of dose switch, and mean change from baseline for values post switch will be summarized separately, as described in Section 11.1. The original study baseline will be used for calculating change from baseline.

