### **3.0 Long Term Efficacy Analysis**

Missing data could occur due to various reasons, including missing visits/assessments, early withdrawal from the study, or missing due to COVID-19 infection or logistic restriction. The probability of having missed visits and missing data due to COVID-19 infection or logistical restrictions related to the COVID-19 pandemic can be reasonably assumed to be unrelated to the unobserved values. Therefore, for the purpose of statistical analysis, it is reasonable to assume that these missing data are missing at random (MAR) and the statistical models that require MAR assumption are appropriate.

As described in Section 9.1.2, longitudinal analysis models MMRM and GLMM will be used for long term efficacy analysis and will be maintained for long term efficacy analysis in the presence of missing data due to COVID-19.

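### Long-term efficacy rows named for 30 mg will carry open-label 15 mg data, and no efficacy output is split at the Amendment 6 dose switch

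*SAP*

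**What the plan says.** Protocol 8.1 leaves the matter to the SAP: "The details for handling the change in dose in analysis will be described in the Statistical Analysis Plan (SAP) for final reporting". SAP 9.1.1 lists four randomised sequences. Sequence 2 is named for 30 mg and sequence 4 for placebo followed by 30 mg. It then states that "for treatment sequences 2 and 4, data collected after dose switch will continue to be summarized under the same treatment sequences". It also says that the first and last switch visits will be noted in the summary, and that there will be no testing.

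The long-term data basis is As Observed (SAP 9.1.2): "Regardless of treatment switching or premature discontinuation of study drug, all observed data will be used in the analysis". SAP 9.3 and Table 5 give descriptive statistics, MMRM or GLMM estimates and plots, all by randomised sequence. The models contain treatment, visit, their interaction and prior bDMARD use, with no term for current dose or for the switch. Appendix B confirms that "longitudinal analysis models MMRM and GLMM will be used for long term efficacy analysis" and adds no split.

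On the timing of the switch, SAP 7.0 plans a disposition table: for subjects on 30 mg in Period 2, "the number and percentage of subjects switching to upadacitinib 15 mg QD at each visit will be summarized". On the safety side the data are separated. For example, SAP 10.3.3.1 says that mean change in laboratory values for switchers "will be censored at the time of dose switch, and mean change from baseline for values post switch will be summarized separately".

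**The concern.** The Period 2 objective (SAP 4.1) names the long-term efficacy of each dose. A reader who follows the 30 mg curve for ACR20/50/70, low disease activity or remission to Week 260 would take it as efficacy on 30 mg. At visits between the first and last switch visits, that curve mixes two doses. After the last switch visit, nobody contributing to it is taking 30 mg. The 30 mg safety results reported alongside stop at the switch, so efficacy and safety carrying the same dose name describe different exposures at late visits. Protocol 5.6.1 had justified Period 2 partly by the absence of dose changes. Amendment 6 removed that condition, but the efficacy row names did not follow.

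**Working it through.** There is no planned figure to reproduce on this point. The check is a comparison of sections, followed by date arithmetic.

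**1. How each long-term output treats the switch**

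| Output | SAP section | At the switch |
|---|---|---|
| Exposure | 8.1 | 30 mg censored; separate group for 15 mg after 30 mg |
| Adverse events | 10.1, 10.2.2 | Same groups as exposure |
| Laboratory and vital signs, mean change | 10.1, 10.3.3.1, 10.4.3 | Censored; later values by visits post switch |
| Potentially significant laboratory values, liver elevations, vital signs | 10.3.3.2, 10.3.3.3, 10.4.3 | Same groups as exposure |
| Efficacy tables, models, plots | 9.1.1, 9.1.2, 9.3, Table 5, Appendix B | No split |

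**2. Which visits can hold 15 mg data**

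Inputs:
- Amendment 6 is dated 16 December 2019 (Protocol 1.1).
- The original protocol is dated 30 September 2015 (Protocol 1.1).
- Period 1 reporting was completed in 2017 (SAP Appendix B, 1.0), and that analysis follows completion of Week 12 by all subjects (SAP 4.4).

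Latest possible baseline: 31 December 2017 minus 12 weeks = 8 October 2017. Time to Amendment 6 is 799 days / 7 = 114.1 weeks. That subject's Week 108 target is 3 November 2019, before the amendment even with the 7-day visit window.

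Earliest possible baseline: 30 September 2015. Time to Amendment 6 is 1,538 days / 7 = 219.7 weeks. That subject's Week 228 target is 12 February 2020, after the amendment even with the window.

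Period 2 has 22 visits (Weeks 16, 20, 24, 36, 48, every 12 weeks to 240, and 260):
- Weeks 16 to 108, 10 visits: before Amendment 6 for every subject.
- Weeks 120 to 216, 9 visits: can fall on either side.
- Weeks 228, 240 and 260, 3 visits: after its date for every subject.

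So at most 9 + 3 = 12 visits, from Week 120, can hold 15 mg data. If the switch follows that visit's assessments, it is 11 visits, from Week 132. This is an outer bound. Falling after the amendment's date does not mean that the subject had switched. Site roll-out dates are not given, and a regional Amendment 6.01 is dated 6 March 2020. The share still on 30 mg at any visit would need assumed enrolment and roll-out, so none is given here.

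**3. How many subjects**

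Planned sizes are 200 (sequence 2) + 100 (sequence 4) = 300 of 600. This is a ceiling, because subjects off drug before Amendment 6 never switch.

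**4. What a mixed row shows**

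Among subjects on drug, if a share s has switched, the row reads (1 − s) × p30 + s × p15. With assumed rates of 0.70 on 30 mg and 0.60 on 15 mg, the row moves from 0.70 (s = 0) through 0.65 (s = 0.5) to 0.60 (s = 1). With 0.50 and 0.60 it rises from 0.50 to 0.60. With equal rates it does not move. Neither direction nor size follows from the documents.

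**5. Why censoring at the switch alone is not enough**

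SAP 4.2 says that "subjects who prematurely discontinue study drug treatment should continue to be followed for all regularly scheduled visits as outlined in the protocol", and As Observed data keep those values. Subjects who stopped 30 mg but stayed in follow-up never reach a switch date. After the last switch visit, a row censored only at the switch would hold off-drug subjects alone.

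**The case against.** The case for the plan is strong. The protocol delegated the choice and the SAP made it openly. The analysis is descriptive and follows randomisation, as efficacy does throughout. The switch-visit note sits inside the efficacy summary, and the disposition table gives counts by visit, so wholly pre-switch and wholly post-switch visits can be identified. The treatment-by-visit interaction does not force post-switch means onto earlier visits.

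The contrast with safety is also partly by design. Safety follows treatment received. Even without Amendment 6, exposure and adverse-event groups pool placebo switchers with subjects who started on each dose, and treatment-emergent events end 30 days after the last dose while efficacy keeps off-drug values. Splitting efficacy at the switch would not put the two on one basis. Finally, no analysis can describe 30 mg efficacy once nobody takes it, and switch-censored model estimates at late visits would rest on off-drug subjects and missing-at-random extrapolation.

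All of this stands, and it limits the remedy. It does not answer three things: the row names still state a dose that switched subjects no longer take, the note locates the mixed visits but cannot separate the data within them, and efficacy by time since switch is not shown at all.

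**Conclusion.** The point holds as a cheap improvement in labelling and supplementary reporting. From Week 120 at the earliest, rows named for 30 mg can contain 15 mg data. After the last switch visit they contain no on-30 mg data and do not address the Period 2 objective for that dose. Weeks 16 to 108 are clean. The bounds rest on the documented amendment and reporting dates; actual switch dates are not in the documents.

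A reader might infer more, and the documents do not support it:
- **That the SAP contradicts the protocol or itself.** The protocol delegated the rule, and the rule is explicit.
- **That long-term 30 mg efficacy is biased by a known amount or in a known direction.** The switch shares and response rates by dose are not given.
- **That the main results are affected.** Period 1 and the alpha-controlled results were completed under SAP version 2.0, and version 3.0 governs only later long-term reporting (SAP 11.1).

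**What to change.** Keep the randomised-sequence tables, models and plots. Rename sequence 2 as *30 mg → 15 mg* and sequence 4 as *Placebo → 30 mg → 15 mg*, and mark the first and last switch visits on the plots.

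For key endpoints, add one supplementary descriptive As Observed table for these two sequences, in two parts:
- **(a) Before the switch:** values up to the first open-label 15 mg dose, restricted to subjects still on 30 mg, with n at each visit, ending no later than the last switch visit.
- **(b) After the switch:** values by visits since switch, using the layout that SAP 10.1 already sets for laboratory values and vital signs.

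Do not add switch-censored MMRM or GLMM estimates beyond visits with on-30 mg data. Aligning sequences 1 and 3 on their own move to open-label is optional and would need an extra derived date.

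Footnote that late pre-switch rows are small and selected, and that post-switch change cannot be attributed to dose. On blinding, Protocol 5.5.5.1 says: "Study sites and subjects will no longer be blinded after this point". COVID-19 also disrupted visits (Protocol 5.3.1, SAP Appendix B), and background therapy may change after Week 24 (Protocol 5.2.3.1).

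The cost is SAP wording and a few extra tables. Switch dates are already needed for disposition, exposure and safety, and no completed analysis is reopened. The downside is some small, selected late rows.
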